## 12.5 Study Design

This is a substudy to a phase I, open-label, dose-ranging clinical trial to assess a third mRNA-1273 vaccination, administered via an IM injection at a dosage of 100 mcg/0.5 mL, in subjects, 18 years of age and older, who received both the first and second mRNA-1273 vaccinations in the main study (see [Table 13](#)) and meet all other substudy eligibility criteria. This optional third mRNA-1273 vaccination substudy is designed to assess safety, reactogenicity, and immunogenicity through 12 months post third vaccination (Substudy Day 366). Subjects who participate in this substudy are from the same three domestic clinical research sites that enrolled into the main study.

**Table 13: Treatment Arms and Substudy Dosing**

Cohort	Sample Size**	Stratum (Years of Age)	First and Second Dose in Main Study	Optional Third Dose in Substudy
1	15	18-55	25 mcg mRNA-1273	100 mcg mRNA-1273
2	15	18-55	100 mcg mRNA-1273	100 mcg mRNA-1273
3	15	18-55	250 mcg mRNA-1273	100 mcg mRNA-1273
4	10	56-70	25 mcg mRNA-1273	100 mcg mRNA-1273
5	10	56-70	100 mcg mRNA-1273	100 mcg mRNA-1273
6*	10	56-70	250 mcg mRNA-1273	n/a
7	10	≥71	25 mcg mRNA-1273	100 mcg mRNA-1273
8	10	≥71	100 mcg mRNA-1273	100 mcg mRNA-1273
9*	10	≥71	250 mcg mRNA-1273	n/a
10	15	18-55	50 mcg mRNA-1273	100 mcg mRNA-1273
11	10	56-70	50 mcg mRNA-1273	100 mcg mRNA-1273
12	10	≥71	50 mcg mRNA-1273	100 mcg mRNA-1273
13*	15	18-55	10 mcg mRNA-1273	n/a

\*Cohorts 6, 9 and 13 were not enrolled.

\*\*\*Four subjects did not receive the second dose of mRNA-1273 in the main study. Three subjects discontinued due to an AE (hives on lower extremities judged related to the first mRNA-1273 vaccination [cohort 1], sore throat [cohort 3], and maculopapular rash [cohort 5]); the other subject discontinued treatment due to quarantine for a COVID-19 exposure (cohort 1).

The third mRNA-1273 vaccination will be offered to subjects who received 2 doses of 25 or 50 mcg (cohorts 1, 4, 7, 10, 11, and 12), which are lower than the EUA mRNA-1273 dosage of 100

mcg, as soon as feasible after their Main Study Day 209 visit, and also will be offered to subjects who received 2 doses of 100 and 250 mcg (cohorts 2, 3, 5, and 8) no later than the close of the window for their originally scheduled Main Study Day 394 visit.

Subjects who receive the third mRNA-1273 vaccination will exit the Schedule of Activities for the main study and will enter the Schedule of Activities for the optional third mRNA-1273 vaccination substudy (see [Table 14](#)). Substudy follow-up visits will occur 1, 2 and 4 weeks post the third mRNA-1273 vaccination (Substudy Days 8, 15, and 29), as well as 3, 6 and 12 months after the third mRNA-1273 vaccination (Substudy Days 91, 181 and 366). Blood will be drawn at these substudy visits for immunogenicity assays. As with prior mRNA-1273 vaccinations, reactogenicity will be measured by the occurrence of solicited injection site and systemic reactions from the time of the third mRNA-1273 vaccination through 7 days after the third mRNA-1273 vaccination. Unsolicited non-serious AEs will be collected from the time of the third mRNA-1273 vaccination through 28 days after the third mRNA-1273 vaccination. SAEs, Protocol Specified AESIs, MAAEs, and NOCMCs will be collected from the time of first mRNA-1273 vaccination through 12 months after the third mRNA-1273 vaccination.

Subjects who do not participate in this substudy, including those who are not eligible to participate in the substudy due to their prior receipt of an FDA authorized (under an EUA) or approved COVID-19 vaccine outside of this clinical trial, will continue, with their permission, to be followed according to the Schedule of Activities for the main study (see [Table 4](#)).

Interim safety and immunogenicity data from this substudy may be reviewed as needed, at the discretion of the study team, to inform public health decisions and to assess the adequacy of the immune responses in the 25 and 50 mcg dose cohorts compared with the 100 mcg dose cohort. Information from interim data reviews may be disseminated to public health officials and partners as needed and included in publications and presentations to inform the global scientific community.

Evaluation of immunogenicity will include quantitation of antibodies to the SARS-CoV-2 S protein at multiple timepoints post third mRNA-1273 vaccination as measured by ELISA and virus neutralization assays. In addition, exploratory studies to characterize T cell responses are planned.

Subjects who participate in the optional third mRNA-1273 vaccination substudy will exit the Schedule of Activities for the main study between Visit 13 and the close of the window for Visit 14 and will not have Visit 14, instead will have Visit 14A and subsequent substudy visits (see [Table 14](#)).

**Table 14: Schedule of Activities for the Optional Third mRNA-1273 Vaccination Substudy**

Optional Third mRNA-1273 Vaccination Substudy Schedule Day		D1	D8	D15	D29	D91	D181	D366
SubStudy Visit Window (± number of days)		n/a	2d	2d	4d	10d	12d	30d
Optional Third mRNA-1273 Vaccination Substudy Visit		V14A	V15	V16	V17	V18	V19	V20
Clinical Evaluations and Procedures	Tube							
Review eligibility criteria for the third mRNA-1273 vaccination		X						
Review medical history and con meds		X	X	X	X	X	X	X
Vital signs		X	X	X	X	{X}	{X}	{X}
Third mRNA-1273 Vaccination		X						
Targeted physical exam		{X}	{X}	{X}	{X}	{X}	{X}	{X}
Evaluate vaccination site		X	X					
Review memory aid			X					
Solicited AEs		X	X					
Unsolicited AEs and SAEs		X	X	X	X 	X 	X 	X 
Pregnancy test (urine) 		X						
Serum for humoral immunogenicity assays (mL)	SST	24	24	24	24	24	24	24
Serum for secondary research (mL)	SST	8	8	8	8	8	8	8
PBMC isolation for cellular immunology assays and plasma (mL)	NaCit CPT	40		30	30	30	30	40
PBMC isolation and plasma for secondary research	NaCit CPT	48	40	18	34	34	34	40
Total volume per visit (mL)		120	72	80	96	96	96	112
Maximum cumulative blood volume (mL) (prior 56 days)		192	264	344	440	96	96	112

{ } Required at this substudy visit only if clinically indicated.

- 1) 0.5 mL of the mRNA-1273 vaccine will be injected IM in the deltoid muscle. After the injection, subjects will be observed for 60 minutes. The injection site will be evaluated, and vital signs obtained, during that period and before the subject leaves the clinic.
- 2) After Substudy Day 29 through the end of the substudy (Substudy Day 366), only SAEs, Protocol Specified AESIs, MAAEs, and NOCMCs will be reported as AEs.
- 3) For women of childbearing potential. Must be confirmed as negative prior to the third mRNA-1273 vaccination. The visit will also include review of contraceptive/menstrual history and pregnancy avoidance counselling.

- 4) For purposes of estimating the maximum possible cumulative blood volume over the prior 56 days, this calculation assumes that the blood draw (72 mL) for Main Study Day 209 occurs on the day prior to Substudy Day 1.

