#### **8.3.5 Time Period and Frequency for Event Assessment and Follow-Up**

For this study:

- solicited AEs will be collected from Days 1-8 (7 days post first vaccination) and Days 29-36 (7 days post second vaccination).
- unsolicited AEs will be collected from Days 1-57.

- SAEs, Protocol Specified AESIs, MAAEs, and NOCMCs will be collected from Day 1 through the end of the study (Day 394).

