## 12.4 Objectives and Endpoints

**Table 12: Objectives and Endpoints (Outcome Measures)**

OBJECTIVES	ENDPOINTS (OUTCOME MEASURES)
Primary	

 
To evaluate the safety and reactogenicity of a third mRNA-1273 vaccination, at a dosage of 100 mcg.
 
	
 
Frequency and grade of each solicited local and systemic reactogenicity AE during a 7-day follow-up period post third mRNA-1273 vaccination.
 
Frequency and grade of any unsolicited AEs during the 28-day follow-up period post third mRNA-1273 vaccination.
 
Frequency of any SAEs, Protocol Specified AESIs, NOCMCs, and MAAEs from Substudy Day 1 to Substudy Day 366.
 

Secondary	

OBJECTIVES	ENDPOINTS (OUTCOME MEASURES)

 
To evaluate the immunogenicity as measured by IgG ELISA to the SARS-CoV-2 S (spike) protein following a third mRNA-1273 vaccination, at a dosage of 100 mcg, at all timepoints after the third mRNA-1273 vaccination.
 
	
 
GMT of antibody at each timepoint after the third mRNA-1273 vaccination.
 
Percentage of subjects who seroconverted, defined as a 4-fold change in antibody titer from the pre-third mRNA-1273 dose baseline (Substudy Day 1) at each post-vaccination timepoint and pre-first mRNA-1273 dose baseline (Main Study Day 1).
 
The GMFR in IgG titer from the pre-third mRNA-1273 dose baseline (Substudy Day 1) at each post-vaccination timepoint and pre-first mRNA-1273 dose baseline (Main Study Day 1).
 

Exploratory	

 
To evaluate the immunogenicity as measured by pseudovirus neutralization and other viral neutralization assays following a third mRNA-1273 vaccination, at a dosage of 100 mcg.
 
	
 
GMT of Neut antibody at each timepoint after the third mRNA-1273 vaccination.
 
Percentage of subjects who seroconverted, defined as a 4-fold change in Neut antibody titer from the pre-third mRNA-1273 dose baseline (Substudy Day 1) at each post-vaccination timepoint and pre-first mRNA-1273 dose baseline (Main Study Day 1).
 
The GMFR Neut antibody titer from the pre-third mRNA-1273 dose baseline (Substudy Day 1) at each post-vaccination timepoint and pre-first mRNA-1273 dose baseline (Main Study Day 1).
 

OBJECTIVES	ENDPOINTS (OUTCOME MEASURES)

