## 12.10 Adverse Events and Serious Adverse Events

### 12.10.1 Reporting of Adverse Events

Reporting of all AEs, solicited and unsolicited, will occur during the period from administration of the third mRNA-1273 vaccine on Substudy Day 1 through Substudy Day 29.

Solicited AEs (i.e., reactogenicity) will be collected using a memory aid and recorded on the appropriate DCF from the time of the third mRNA-1273 vaccination through 7 days post third mRNA-1273 vaccination (Substudy Days 1-8).

Unsolicited AEs of all severities will be reported from the time of the third mRNA-1273 vaccination on Substudy Day 1 through Substudy Day 29.

After Substudy Day 29 through the end of the substudy (Substudy Day 366), only SAEs, Protocol Specified AESIs, MAAEs, and NOCMCs will be reported as AEs.

SAEs, Protocol Specified AESIs, MAAEs, and NOCMCs will be collected from Substudy Day 1 through the end of the substudy (Substudy Day 366).

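### Substudy windows let V15 and V17 fall before the adverse-event periods they close; no solicited-AE review is scheduled afterwards, and the reporting rule for onsets on Days 26-29 is unclear

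*Protocol*

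**What the plan says.** Two of the substudy's primary endpoints run over fixed periods after the third dose. Table 12 sets a 7-day period for solicited reactions, and for unsolicited events it reads "Frequency and grade of any unsolicited AEs during the 28-day follow-up period post third mRNA-1273 vaccination". Section 12.10.1 turns these into study days. Solicited AEs are collected by memory aid "from the time of the third mRNA-1273 vaccination through 7 days post third mRNA-1273 vaccination (Substudy Days 1-8", and for the rest: "Unsolicited AEs of all severities will be reported from the time of the third mRNA-1273 vaccination on Substudy Day 1 through Substudy Day 29". Section 12.11.8 then asks for solicited severity on each of Substudy Days 1-8 and for the maximum over all 8 days.

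Table 14 schedules the visits. Its row "SubStudy Visit Window (± number of days" gives 2 days for D8 and D15, 4 days for D29 and 10 days for D91. The row "Review memory aid" is marked at V15 only, and the solicited-AE row at D1 and V15 only. The row for unsolicited AEs and SAEs is marked at every visit, with footnote 2 attached from V17 onward. That footnote limits AEs after Substudy Day 29 to SAEs, Protocol Specified AESIs, MAAEs and NOCMCs. Table 14 lists no telephone contacts.

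**The concern.** V15 is the only visit that reviews the diary. V17 is the last visit before a gap of about two months. Each closes a primary safety period, yet each may be held before that period ends. Because such a visit is within window, no out-of-window deviation would mark the record as short.

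At stake is the completeness of two descriptive safety summaries for a third dose that Section 12.3.1 says had not been evaluated in humans. For solicited reactions the question is whether the last two daily grades are reviewed at all. For unsolicited events it is whether non-serious events starting in the last four days are recorded reliably. The windows are also looser than those for Doses 1 and 2 in Table 4: ±1 day at Visits 04 and 09, and ±2 days at Visit 11.

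**Working it through.** **Inputs.** Windows: Table 14. Collection periods: Section 12.10.1. Carry-over of main-study rules unless Section 12 says otherwise: opening of Section 12. Interim history covering changes since the previous contact: Section 8.2. Vaccination is Substudy Day 1. The day of the visit is counted as covered.

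**The plan's own period ends.** Solicited: 1 + 7 = Day 8. Unsolicited: 1 + 28 = Day 29. Both agree with Section 12.10.1.

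**Allowed visit days (nominal day ± window).**
- V15: 8 ± 2 = Days 6 to 10
- V16: 15 ± 2 = Days 13 to 17
- V17: 29 ± 4 = Days 25 to 33
- V18: 91 ± 10 = Days 81 to 101

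**Days left open by the earliest compliant visit.**
- V15 on Day 6: 8 - 6 = 2 days (Days 7-8), or 2/8 = 25% of the solicited period.
- V17 on Day 25: 29 - 25 = 4 days (Days 26-29), or 4/29 = 13.8% of the unsolicited period.

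These are worst cases for one subject, not expected losses.

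**What later contacts cover after a Day 6 V15.**
- V16 follows 13 - 6 = 7 to 17 - 6 = 11 days later. It has an AE row without footnote 2 and a history review. Section 12.10.1 keeps all AE reporting open to Day 29: "Reporting of all AEs, solicited and unsolicited, will occur during the period from administration of the third mRNA-1273 vaccine on Substudy Day 1", running to that day. An event on Day 7 or 8 can therefore be recorded as an AE.
- No memory-aid or solicited-AE row is marked at V16, so no scheduled step yields the daily grades that Section 12.11.8 needs.
- The main-study calls fall 1 and 2 days after dosing. If they carry over, they come before Day 6.
- Section 8.3.1.1 has clinicians follow reactions unresolved at 7 days. That covers persisting symptoms, not new ones starting on Days 7-8.

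**What later contacts cover after a Day 25 V17.**
- V18 follows 81 - 25 = 56 to 101 - 25 = 76 days later.
- Recall for an onset on Days 26-29 runs from 81 - 29 = 52 to 101 - 26 = 75 days.
- If footnote 2 applies by date of onset, the event is still reportable at V18. If it applies by date of report, a non-serious event that is not an AESI, MAAE or NOCMC is lost. The text does not say which.

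**Comparison with the main study.** Earliest compliant visits are 8 - 1 = Day 7, 36 - 1 = Day 35 and 57 - 2 = Day 55, which is 1, 1 and 2 days early. The feature is the same but smaller.

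**The case against.** The strongest reply is that a visit date does not end a collection period. The periods are defined by time since vaccination, and subjects keep the memory aid for 7 days whenever they attend. This stands, and it limits the solicited problem to review of the last two days: the diary may be filled in, but no one is scheduled to go through it.

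A reader might infer that no later contact picks up the missed days. The documents do not support that. V16 asks about AEs and interim history inside the Day 29 limit, and V18 still carries an AE row.

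The onset-date reading of footnote 2 is also the more sensible one. The footnote is attached to V17 itself, so on a report-date reading a compliant V17 on Days 30-33 could record no ordinary non-serious AE. On the onset-date reading the Days 26-29 problem is long recall, not loss. That argues for stating the reading, since the text leaves both open.

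A reader might also infer that the main study cuts unsolicited follow-up short when Dose 2 is late. With Visit 06 on Day 31, 28 days later is Day 59, while Section 8.3.5 reads "unsolicited AEs will be collected from Days 1-57". But Table 4 footnote f ties Visit 11 to the actual Visit 06 date, and Sections 8.3.1 and 9.4.4 already say 28 days after the second vaccination. What remains is a label to harmonise.

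Finally, the substudy is descriptive and tests no hypothesis (Section 12.11.1). That lowers the stakes without removing the gap.

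**Conclusion.** The point holds in this form. The windows allow V15 and V17 up to 2 and 4 days before the periods they close. An early V15 leaves the grades for Days 7-8 without a scheduled review. An early V17 leaves non-serious onsets on Days 26-29 to 52-75 days' recall under an ambiguous reporting rule.

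Any under-capture is limited to early attenders. It is probably small, particularly for maximum solicited severity if most reactions peak early, which is a judgement and not a figure from the plan. Its size cannot be computed, because the documents do not say how many subjects attend early. SAEs, Protocol Specified AESIs, MAAEs and NOCMCs are collected to Substudy Day 366 and are unaffected.

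It would be too strong to conclude that third-dose rates are biased downward by a known amount, or that early attenders always count with full denominators. The SAP, written for the two-dose schedule, uses non-missing data as the denominator for maximum severity (Section 9.3.1) and shows a Not Reported row in its daily mock-ups. Whether the substudy will follow this is not stated. This is a cheap improvement to primary safety data, not a flaw that undermines the substudy.

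**What to change.** - In Table 14, set V15 to D8 -0/+2 (Days 8-10) and V17 to D29 -0/+4 (Days 29-33). Both lie inside the current windows and add no visits. V15 still ends three days before V16 can open on Day 13.
- State in footnote 2 that the limit applies by date of AE onset, so that a non-serious event starting by Day 29 is reportable at any later visit.
- In Sections 8.3.1.2 and 8.3.5, align the Day 57 label with 28 days after the second vaccination, as in Sections 8.3.1 and 9.4.4. No main-study visit window needs to change.

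**Cost.** Scheduling is tighter: V15 goes from 5 allowed days to 3, and V17 from 9 to 5. The D8 and D29 blood samples come slightly later. The window midpoints move from Day 8 to Day 9 and from Day 29 to Day 31. Actual study day is already a column in the SAP's immunogenicity listing (Listing 8), and keeping it for the substudy would make the shift visible.

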## 12.6 Eligibility Criteria

### 12.6.1 Inclusion Criteria

A subject must meet all the following criteria to be eligible to participate in this substudy:

1. Enrolled in the main study and received both the first and second mRNA-1273 vaccinations.
2. Provides written informed consent for the third mRNA-1273 vaccination.
3. Agrees to the collection of venous blood per substudy.
4. Must agree to have samples stored for secondary research.
5. Women of childbearing potential have had a negative urine pregnancy test within 24 hours before the third mRNA-1273 vaccination.
6. Women of childbearing potential must agree to use or have practiced true abstinence or use at least one acceptable primary form of contraception.

*Note: These criteria are applicable to females in a heterosexual relationship and child-bearing potential (i.e., the criteria do not apply to subjects in a same sex relationship).*

*Not of childbearing potential – post-menopausal females (defined as having a history of amenorrhea for at least one year) or a documented status as being surgically sterile (hysterectomy, bilateral oophorectomy, tubal ligation/salpingectomy, or Essure® placement).*

*True abstinence is 100% of time no sexual intercourse (male's penis enters the female's vagina). (Periodic abstinence [e.g., calendar, ovulation, symptothermal, post-ovulation methods] and withdrawal are not acceptable methods of contraception).*

*Acceptable forms of primary contraception include monogamous relationship with a vasectomized partner who has been vasectomized for 180 days or more prior to the subject's first vaccination, intrauterine devices, birth control pills, and injectable/implantable/insertable hormonal birth control products.*

*Must use at least one acceptable primary form of contraception for at least 30 days prior to the third mRNA-1273 vaccination and for at least 30 days after the third mRNA-1273 vaccination.*

### 12.6.2 Exclusion Criteria

A subject who meets any of the following criteria will be excluded from participation in this substudy.

1. Anaphylaxis or other systemic hypersensitivity reaction following a mRNA-1273 or any other vaccination.
2. Immediate allergic reaction of any severity after mRNA-1273 or any of its components.

Including polyethylene glycol (PEG)

3. Immediate allergic reaction of any severity to polysorbate.

Due to potential cross-reactive hypersensitivity with the vaccine ingredient PEG

4. History of an SAE judged related to mRNA-1273 vaccine.
5. Female subject who is breastfeeding or plans to breastfeed from the time of the third mRNA-1273 vaccination through 30 days after the third mRNA-1273 vaccination.
6. Has an acute illness, as determined by the participating site PI or appropriate sub-investigator, with or without fever [oral temperature  $\geq 38.0^{\circ}\text{C}$  ( $100.4^{\circ}\text{F}$ )], within 72 hours prior to the third mRNA-1273 vaccination.

An acute illness which is nearly resolved with only minor residual symptoms remaining is allowable if, in the opinion of the participating site PI or appropriate sub-investigator, the residual symptoms will not interfere with the ability to assess safety parameters as required by the substudy.

7. Has received any approved, authorized or investigational COVID-19 vaccine outside of this trial.
8. Any clinically significant medical condition that, in the opinion of the investigator, poses an additional risk to the subject from vaccination.
9. History of documented COVID-19 infection.
10. Has any medical disease or condition that, in the opinion of the participating site PI or appropriate sub-investigator, precludes substudy participation.
11. Received or plans to receive a licensed vaccine, other than a COVID-19 vaccine, within 2 weeks before or after the third mRNA-1273 vaccination.

## 12.7 Study Product

### 12.7.1 Study Product Description

#### **Product: mRNA-1273**

For the optional third mRNA-1273 vaccination substudy, mRNA-1273 is provided by ModernaTX, Inc. via the DMID CMS as a sterile solution for injection in a 10 dose multidose vial formulated at a concentration of 0.2mg/mL in 20 mM Tris buffer containing 87 mg/mL sucrose and 4.3 mM acetate, at pH 7.5 and presented in 10R USP Type I borosilicate glass vials with PLASCAP vial seal containing a 20 mm FluroTec-coated plug stopper and aluminum flip-off crimp seals with a nominal fill volume of 6.3 mL/vial.

There is no preservative in the mRNA-1273 solution. Hence, all ten (10) doses must be withdrawn into individual dosing syringes in quick succession, one after the other once the vial is breached.

Dilution is not required for the third mRNA-1273 vaccination. Each multidose vial contains ready-to-use solution and does not require further dilution or preparation. It will be administered as a single 0.5 mL IM injection of 100 mcg into the deltoid muscle.

See the protocol-specific MOP for detailed information:

- 20 (minimum) to 30 (maximum) minutes are required for the mRNA-1273 vials to equilibrate to room temperature (20°C to 25°C).
- A maximum of 30 minutes is allowed between completion of equilibration and completion of dosing syringes fill.
- Ten (10) dosing syringes must be prepared from each mRNA-1273 vial.
- All dosing syringes must be filled in quick succession, one after the other.
- Filled dosing syringes must be held at room temperature (20°C to 25°C) and will expire (eight) 8 hours after being filled.
- Withdrawal of mRNA-1273 from the vial into the dosing syringes should be completed within 30 minutes after the vial has equilibrated to room temperature (20°C to 25°C).

